6.4 Dosage Selected, Preparation, and Schedule of Administration

Treatment will be administered on an outpatient basis.

6.4.1 Supply and packaging

ESK981 monotosylate is a fully synthetic drug substance containing a core indolocarbazolone ring system. ESK981 monotosylate drug substance is a yellow to orange powder that has a molecular weight of 649.77 g/mol. The drug substance contains 73.5% theoretical weight percent of the active moiety ESK981 (free base).

ESK981 drug product is an off-white to orange opaque, hard gelatin capsule containing 40 mg (free base equivalents) of ESK981 monotosylate. The drug product is packaged in a

high-density polyethylene (HDPE) bottle with a child resistant closure and an induction-sealed inner seal. The formulation also contains lactose monohydrate.

6.4.2 Storage and handling

ESK981 capsules should be stored refrigerated at 2°C to 8°C (36°F to 46°F). The stability of the drug substance and drug product continues to be monitored.

6.5 Dose Modifications

Patients with NCI-CTCAE Grade 3 or Grade 4 adverse events judged to be (at least possibly) related to ESK981 will have their ESK981 held until the adverse event resolves to Grade 2 or lower. Standard management of adverse events should be utilized. Patients may then be restarted on ESK981 at a reduced dose of 120mg (3 capsules) daily for 5 days, 2 days off. Following a dose reduction, patients who have a second NCI-CTCAE Grade 3 or Grade 4 adverse event judged to be at least possibly related to ESK981 will be discontinued from the study. If drug cannot be restarted within 3 weeks of being held, ESK981 should be discontinued. Patients will also be discontinued for any of the following reasons:

1. Worsening symptoms that can be attributed to prostate cancer
2. Unacceptable adverse event(s) including development of a urinary outlet obstruction requiring urinary catheterization and/or surgical intervention,
3. Intercurrent illness that prevents further participation,
4. Patient refuses further treatment through the study and/or withdraws consent to participate,
5. Patient is noncompliant with respect to taking drugs, keeping appointments, or having tests required for the evaluation of drug safety and efficacy, or
6. General or specific changes in the patient's condition that render the patient unacceptable for further treatment in this study in the judgment of the investigator.

Under no circumstance will care of a withdrawn patient be adversely affected by a decision to withdraw or be withdrawn from the study

6.6 Management of Expected Toxicities

Event Name	Nausea
Grade of Event	Management/Next Dose
Grade 1	No change in dose
Grade 2	No change in dose
Grade 3-4	Hold until \leq Grade 2. Resume at one dose level lower, if indicated per Section 6.5 .
Recommended management: antiemetics.	

Event Name	Vomiting
Grade of Event	Management/Next Dose
Grade 1	No change in dose
Grade 2	No change in dose
Grade 3-4	Hold until \leq Grade 2. Resume at one dose level lower, if indicated per Section 6.5 .
Recommended management: antiemetics.	

Event Name	Diarrhea
Grade of Event	Management/Next Dose
Grade 1	No change in dose
Grade 2	No change in dose
Grade 3-4	Hold until \leq Grade 2. Resume at one dose level lower, if indicated per Section 6.5 .

Recommended management: Loperamide anti-diarrheal therapy

Dosage schedule: 4 mg at first onset, followed by 2 mg with each loose motion

until diarrhea-free for 12 hours (maximum dosage: 16 mg/24 hours)

Adjunct anti-diarrheal therapy is permitted and should be recorded when used.

Event Name	Neutropenia
Grade of Event	Management/Next Dose
Grade 1	No change in dose
Grade 2	No change in dose
Grade 3-4	Hold until \leq Grade 2. Resume at one dose level lower, if indicated per Section 6.5 .

Recommended management: Use of growth factors is not recommended.

Management of neutropenia should be by dose reduction. For grade 4 febrile neutropenia, discontinue treatment.

Event Name	Anemia
Grade of Event	Management/Next Dose
Grade 1	No change in dose
Grade 2	No change in dose
Grade 3-4	Hold until \leq Grade 2. Resume at one dose level lower, if indicated per Section 6.5 .

Recommended management: Treat by using local standards.

Event Name	Thrombocytopenia
Grade of Event	Management/Next Dose
Grade 1	No change in dose
Grade 2	No change in dose
Grade 3-4	Hold until \leq Grade 2. Resume at one dose level lower, if indicated per Section 6.5 .

Recommended management: Treat by using local standards.

Event Name	Hypertension
Grade of Event	Management/Next Dose
Grade 1	No change in dose
Grade 2	No change in dose
Grade 3-4	Hold until \leq Grade 2. Resume at one dose level lower, if indicated per Section 6.5

Recommended management: Treat by optimizing or adding antihypertensive medications to achieve well-controlled blood pressure of $< 150/90$ mmHg.

Event Name	Left Ventricular Dysfunction
Grade of Event	Management/Next Dose
Grade 1	No change in dose
Grade 2	No change in dose
Grade 3-4	Hold until \leq Grade 2. Resume at one dose level lower, if indicated per Section 6.5 .

Recommended management: Treat by optimizing or adding cardiovascular medications for management of congestive heart failure.

Event Name	Cardiac Arrhythmias
Grade of Event	Management/Next Dose
Grade 1	No change in dose
Grade 2	No change in dose
Grade 3-4	Hold until \leq Grade 2. Resume at one dose level lower, if indicated per Section 6.5 .

Recommended management: Identify appropriate arrhythmias such as atrial fibrillation, atrial flutter, atrioventricular blocks, and other conduction disorders. Treat appropriate medications or procedures as established by standard of care.

Event Name	Fatigue
Grade of Event	Management/Next Dose
Grade 1	No change in dose
Grade 2	No change in dose
Grade 3-4	Hold until \leq Grade 2. Resume at one dose level lower, if indicated per Section 6.5 .

Recommended management: Optimize supportive care.

6.7 Concomitant Medications and Supportive Care

Because of the potential for drug-drug interaction, the concurrent use of all other drugs, over-the-counter medications, and alternative therapies must be documented on the CRF. The principal investigator should be alerted if the patient is taking any agent found in Appendix B (a listing of medications with the potential for drug-drug interaction).

6.7.1 Supportive Care Medications

Patients should receive appropriate supportive care for CRPC and appropriate treatment for comorbidities, subject to the restrictions due to potential drug-drug interactions detailed in Section 6.7.3.

6.7.2 Prohibited before enrollment and during administration of study treatment

Concomitant systemic treatments for CRPC (other than a GnRH agonist/antagonist) are prohibited including: CYP-17 inhibitors (e.g. ketoconazole, abiraterone), antiandrogens (e.g. bicalutamide, nilutamide), second generation antiandrogens (e.g. enzalutamide, ARN-509, Galeterone), immunotherapy (e.g. sipuleucel-T, ipilimumab), and chemotherapy (e.g. docetaxel, cabazitaxel).

6.7.3 Potential for drug-drug interactions

ESK981 is metabolized via CYP1A2, CYP2C8, and CYP3A4. Inhibitors of CYP1A2, CYP2C8, and CYP3A4 have the potential to increase plasma concentration of ESK981. Inducers of

CYP1A2, CYP2C8, and CYP3A4 have the potential to decrease plasma concentrations of ESK981. Concomitant use of a medication known to be a potent inhibitor of CYP1A2, CYP2C8, or CYP3A4 (see Appendix B), or a potent inducer of CYP1A2, CYP2C8, or CYP3A4 (see Appendix B) should be avoided unless deemed to be medically necessary by the investigator. In addition, nonclinical studies have identified the potential for ESK981 to inhibit CYP3A4/5 (K_i 2.2 μ M). ESK981 has the potential to increase plasma concentration of concomitant medications that are CYP3A4/5 substrates. Caution should be used, or alternative treatments considered, if concomitant treatment with CYP3A4/5 substrates that have a narrow therapeutic range is needed (see Appendix B).

7. **SAFETY EVALUATION**

A safety review of the first six patients who have been observed for 8 weeks will occur. Enrollment will pause until all six patients have been assessed for toxicity evaluation.

7.1 **Definitions**

7.1.1 **Adverse Event (AE)**

Any untoward medical occurrence in a patient or clinical investigation subject administered a pharmaceutical product and which does not necessarily have to have a causal relationship with this treatment (ICH E2A). An adverse event for the purposes of this protocol is the appearance of (or worsening of any pre-existing) undesirable sign(s), symptom(s), or medical condition(s) occurring after signing the informed consent even if the event is not considered to be related to the study drug(s). An AE can therefore be any unfavorable and unintended sign (including an abnormal laboratory finding), symptom, or disease temporally associated with the use of a medicinal product, whether or not related to the medicinal product.

An abnormality identified during a medical test (e.g. laboratory parameter, vital sign, ECG data, physical exam) should be defined as an AE only if the abnormality meets one of the following criteria:

- Requires active intervention
- Requires interruption or discontinuation of study medication

The abnormality or investigational value is clinically significant in the opinion of the investigator. An adverse event will be recorded and followed from treatment administration to 30 days post-treatment or resolution.

7.1.2 **Expected Adverse Events**

Expected adverse events are those that have been previously identified as resulting from administration of the agent. An adverse event can be considered expected when it appears in the current adverse event list, the Investigator's Brochure, the package insert or is included in the informed consent document as a potential risk.

7.1.3 **Unexpected Adverse Events**

Adverse reactions are those that the nature or severity of which is not consistent with the applicable product information (e.g., Investigator's Brochure for an unapproved investigational medicinal product) (ICH E2A).

Contact the Principal Investigator or sponsor to confirm unexpected adverse events when necessary.

7.1.4 Adverse Drug Reaction (ADR)

All noxious and unintended responses to a medicinal product related to any dose should be considered adverse drug reactions (ICH E2A).

The phrase "response to a medicinal product" means that a causal relationship between a medicinal product and an adverse event is at least a reasonable possibility, *i.e.*, the relationship cannot be ruled out. "Reasonable possibility" means there is evidence to suggest a causal relationship between the drug and the adverse event.

7.1.5 Serious Adverse Event (SAE)

An SAE/ADR as defined in the Code of Federal Regulations (21 CFR § 312.32) is any event that:

- results in death
- is life-threatening
- results in inpatient hospitalization or prolongation of existing hospitalization
- results in persistent or significant disability or incapacity
- results in congenital anomaly or birth defect
- is medically significant in the opinion of the investigator

Events that are **not** considered serious adverse events include:

- routine treatment or monitoring of the studied indication, not associated with any deterioration in condition, or for elective procedures
- elective or pre-planned treatment for a pre-existing condition that is unrelated to the indication under study and did not worsen since signing the informed consent
- emergency outpatient treatment for an event not fulfilling the serious criteria outlined above and not resulting in inpatient admission
- respite care

7.1.6 Progression of malignancy

Progression of a patient's malignancy should not be considered an AE, unless in the investigator's opinion, study treatment resulted in an exacerbation of the patient's condition. If disease progression results in death or hospitalization while on study or within 30 days of the last dose, progressive disease will be considered an SAE.

7.1.7 Life-threatening

An adverse event or suspected adverse reaction is considered "life-threatening" if, in the view of either investigator or sponsor, its occurrence places the patient or subject at immediate risk of death. It does not include an adverse event or suspected adverse reaction that, had it occurred in a more severe form, might have caused death (FDA 21 CFR § 312.32).

7.1.8 Hospitalization (or prolongation of hospitalization)

Hospitalization encompasses any inpatient admission (even for less than 24 hours) resulting from a precipitating, treatment-emergent adverse event. For chronic or long-term patients, inpatient admission also includes transfer within the hospital to an acute or intensive care inpatient unit. Hospitalizations for administrative reasons or a nonworsening preexisting condition should not be considered AEs (e.g., admission for workup of a persistent pretreatment laboratory abnormality, yearly physical exam, protocol-specified admission, elective surgery). Preplanned treatments or surgical procedures should be noted in the baseline documentation. Hospitalization because of an unplanned event will be deemed an SAE.

Prolongation of hospitalization is any extension of an inpatient hospitalization beyond the stay anticipated or required for the original reason for admission.

7.1.9 Persistent or Significant disability/incapacity

Any AE that results in persistent or significant incapacity or substantial disruption of the patient's ability to conduct normal life functions.

7.1.10 Congenital anomaly

If the female partner of a male patient becomes pregnant during the course of the study, the treating physician must be notified immediately. All confirmed pregnancies must be immediately reported to the sponsor-investigator. All pregnancies will be followed until resolution (*i.e.*, voluntary or spontaneous termination or birth) and assessed for congenital anomalies and birth defects.

7.2 Recording and Grading of Adverse Events

7.2.1 Recording

All observed or volunteered adverse events, regardless of treatment group, severity, suspected causal relationship, expectedness, or seriousness will be recorded on the Medical History/Current Medical Conditions Electronic Case Report Form.

The occurrence of adverse events should be sought by non-directive questioning of the patient at each visit during the study. Adverse events also may be detected when they are volunteered by the patient during or between visits or through physical examination, laboratory test, or other assessments. As far as possible, each adverse event should be evaluated to determine:

- a. The severity grade (CTCAE grade 1-4)
- b. Its relationship to each study drug (suspected/not suspected)
- c. Its duration (start and end dates or if continuing at final exam)
- d. Action taken (no action taken; study drug dosage adjusted/temporarily interrupted; study drug permanently discontinued due to this adverse event; concomitant medication taken; non-drug therapy given; hospitalization/prolonged hospitalization)

Adverse events (but not serious adverse events) occurring before starting study treatment, but after signing the informed consent form are recorded on the Medical History/Current Medical Conditions Electronic Case Report Form. Abnormal laboratory values or test results constitute adverse events only if they induce clinical signs or symptoms, are considered clinically significant or require therapy (e.g., any hematologic abnormality that requires

transfusion or cytokine treatment), and should be recorded on the Adverse Events CRF under the signs, symptoms or diagnosis associated with them. In addition, isolated abnormal laboratory values that are considered clinically significant (e.g., cause study discontinuation or constitutes in and of itself a Serious Adverse Event) should be recorded on the Adverse Events CRF. SAEs occurring after the start of treatment are recorded on the Adverse Event CRF.

A clinically significant change in a physical examination finding or an abnormal test result should be recorded as an AE, if it:

- is associated with accompanying symptoms,
- requires additional diagnostic testing or medical or surgical intervention,
- leads to a change in study dosing or discontinuation from the study,
- requires additional concomitant drug treatment or other therapy, or
- is considered clinically significant by the investigator.

An abnormal test result that is subsequently determined to be in error does not require recording as an adverse event, even if it originally met one or more of the above criteria.

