11.2 Endpoints

11.2.1 The first primary endpoint (PSA50) is a PSA decline of $\geq 50\%$ from baseline (PSA50), using the PCWG3 criteria. Refer to Section 8.2.1.

The second primary endpoint(s) (toxicities) is (are) defined in Section 7. Adverse events of all grades will be captured by the National Cancer Institute - Common Terminology Criteria for Adverse Events, version 4.03 (NCI-CTCAE v4.03) and GCP standards.

11.2.2 The secondary endpoints are defined as follows:

Time to PSA response (TTPR) is defined as the time from treatment start until the first documented occurrence of PSA50. PSA50 is defined in Section 1.3.

Duration of PSA response (PRD) is defined as the time from start of PSA50 until PSA progression (defined in Section 8.3.2).

PSA progression free survival (PPFS) is defined in Section 8.3.2 except that it will be based on PSA assessments only. PSA progression rates will be estimated from the PSA-only PFS distribution.

11.2.3 The correlative/exploratory/tertiary endpoints (and the methods of their determination) are described in Section 9.

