11.4 Analysis

11.4.1 For the Primary Objectives, all analyses point and (1-sided Wilson type 90% lower) CI estimates of the primary endpoint (PSA50) will be calculated.

Adverse events will be tabulated by incidence and severity graded according to the National Cancer Institute – Common Terminology Criteria for Adverse Events (CTCAE) version 4.03. Other statistics will include point and (2-sided) CI estimates of overall toxicity and of specific types of toxicity.

11.4.2 For Secondary Objective 1, descriptive statistics of TTPR will be used to summarize the time to PSA response. These descriptives will include N, median, mean, standard deviation (SD), interquartile range (IQR), minimum, and maximum.

11.4.3 For Secondary Objectives 2 and 3, the censored distributions of duration of response (RD) and PSA progression free survival (PFS) will be summarized with the Kaplan-Meier (K-M) survivorship estimate. A graph of the K-M curve for PRD and for PPFS will be generated along with the Hall-Wellner 90% confidence band, and a display of the number of patients at risk at several time points, below the X-axis. Summary statistics (6-month rate, 12-month rate, median, etc.) will be calculated from the K-M life table, each one with its respective 80% confidence interval (CI).

11.4.4 For the Correlative (Exploratory) Objectives, frequency distributions of all categorical variables (grade of specific types of toxicity, and categorical biomarkers or other correlatives) will be generated. Serial PSA levels will be displayed using spaghetti plots, and changes in PSA using waterfall plots.

Descriptive statistics will be used to summarize all continuous correlatives (e.g., PSA, continuous biomarkers and other correlatives), and changes in them pre/post ESK981 treatment. Gene expression levels will be \log_2 transformed prior to descriptive analysis. Multiple boxplots and scatterplots will be used to display summary statistics of biomarkers/correlatives and interrelationships between continuous correlatives, respectively.

Details of the planned determination of bioinformatics correlatives are given in Section 9. Response (whether PSA50 or overall), a categorical clinical outcome, will be statistically modeled as a function of each correlative using exact logistic regression. TTPR, a continuous

uncensored clinical outcome (limited to only the PSA50 responders), will be statistically modeled as a function of each correlative using linear regression.

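### Laboratory toxicity reaches the primary safety tabulation only through adverse-event recording, never by CTCAE grade alone, so some graded values can be undercounted

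*Combined protocol and SAP*

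**What the plan says.** **Endpoint.** Section 11.1 makes safety and tolerability the second primary objective. Section 11.2.1 says the toxicity endpoint is defined in Section 7 and adds: "Adverse events of all grades will be captured". Section 11.4.1 gives the analysis: "Adverse events will be tabulated by incidence and severity graded according to the National Cancer Institute". It also plans two-sided confidence intervals for overall and specific toxicities, and Section 11.4.4 adds frequency distributions of toxicity grade.

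**When a laboratory value is an AE.** Two sections answer this.
- Section 7.1.1: an abnormal test "should be defined as an AE only if the abnormality meets one of the following criteria". The criteria are a need for active intervention, "Requires interruption or discontinuation of study medication", and clinical significance in the investigator's opinion.
- Section 7.2.1: "Abnormal laboratory values or test results constitute adverse events only if they induce clinical signs or symptoms, are considered clinically significant or require therapy". A later list in the same section also makes an abnormal result recordable if it has accompanying symptoms, needs more testing or treatment, is judged clinically significant, or "leads to a change in study dosing or discontinuation from the study".

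**Dosing rules that refer to laboratory grades.** Section 6.5: "Patients with NCI-CTCAE Grade 3 or Grade 4 adverse events judged to be (at least possibly) related to ESK981 will have their ESK981 held". Section 6.6 lists ten expected toxicities. Three are laboratory findings (neutropenia, anemia, thrombocytopenia). Each has a Grade 3-4 row that holds drug with no symptom condition, and Grade 1-2 rows with no dose change.

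**Data collected.** Appendix C schedules a complete blood count and chemistry panel at screening, on Days 8, 15 and 22 of Cycle 1, on Day 1 of each later cycle, and at the end-of-treatment visit 30 days after the last dose.

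**The concern.** The plan collects objective, repeatedly measured safety laboratory data, but the primary safety analysis sees them only after an AE filter that contains no grade threshold. Where the filter comes down to clinical significance, two men with the same blood result can be counted differently. The filter can drop a graded abnormality but cannot add one, so any error against the measured grades is downward.

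This matters because laboratory toxicity is a recognized risk of this drug. Section 1.2 reports Grade 3/4 neutropenia in the highest-dose Phase I cohorts, and three of the ten toxicities in Section 6.6 are cytopenias. The trial has one arm, so no control group would show under-recording. Section 7 also pauses enrollment for a safety review of the first six patients. If that review relies on recorded AEs, it inherits the same filter.

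**Working it through.** No stated figure in the plan depends on the AE rule, so the main check is to follow each kind of laboratory value through the text.

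**Step 1. Compare the two tests.** Section 7.1.1 admits intervention, drug interruption or discontinuation, and investigator-judged significance. The opening sentence in 7.2.1 admits symptoms, significance and therapy, and omits dosing; its later list restores dosing change and adds diagnostic testing. They overlap heavily. But two exclusive rules with different contents cannot both be applied literally: a value that prompts only extra testing qualifies under the 7.2.1 list and not under 7.1.1. Neither section uses CTCAE grade as a criterion.

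**Step 2. Trace each kind of value, assuming no symptoms.**

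| Laboratory finding | Dosing rule | Route into the AE table |
|---|---|---|
| Grade 3-4 neutropenia, anemia or thrombocytopenia, during dosing | 6.6 row: hold on grade | The hold is an interruption (7.1.1) and a dosing change (7.2.1 list), so it is an AE |
| Grade 1-2 of the same three | 6.6 row: no change in dose | No dosing route; therapy, further testing or opinion only |
| Grade 3-4 of a parameter with no 6.6 row (ALT, AST, creatinine, lymphocytes where reported) | Only 6.5, which acts on adverse events | 6.5 presupposes an AE; therapy, further testing or opinion must supply it |
| Any grade first seen at the end-of-treatment visit | No dose left to change | No dosing route; therapy, further testing or opinion only |

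For neutropenia the therapy route is narrow, since Section 6.6 says "Recommended management: Use of growth factors is not recommended".

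**Step 3. Look for a second route into the analysis.** Sections 11.4.1 and 11.4.4 count toxicities, which 11.2.1 defines by Section 7. The continuous summaries in 11.4.4 cover PSA, biomarkers and other correlatives. No table of graded results from the scheduled blood count and chemistry panel is specified.

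**Step 4. Size.** Let p be the true proportion of men with a given finding in one of the last three rows, and f the share of those men with no qualifying AE record.

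Reported rate = p(1 − f), so reported/true = 1 − f whatever p is.

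The documents give neither p nor f. For an illustration, take the planned maximum enrollment: 27 / (1 − 0.15) = 31.8, rounded up to 32, which reproduces Section 11.3.4. Assume all 32 men are in the safety analysis, p of 10% to 30%, and f of 25% or 50%.

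| Assumed p | True expected cases (32p) | Recorded, f = 25% | Recorded, f = 50% |
|---|---|---|---|
| 10% | 3.2 | 2.4 | 1.6 |
| 20% | 6.4 | 4.8 | 3.2 |
| 30% | 9.6 | 7.2 | 4.8 |

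For the six-patient review, if it used AE records only, the chance of no recorded case is (1 − p(1 − f))^6. At p = 20% this is 0.80^6 = 0.26 with full recording, 0.85^6 = 0.38 with f = 25%, and 0.90^6 = 0.53 with f = 50%.

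These are assumed values. They do not apply to the first row of the Step 2 table.

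**The case against.** The best defense is that the protocol captures what matters most. The three cytopenias have grade-based holds, the hold makes the value an AE, and in practice a Grade 3-4 liver or renal value will often prompt a repeat test or treatment, which also qualifies. Filtering minor laboratory changes by clinical significance is a legitimate choice, and the promise to capture all grades can fairly be read as every grade of an event that already qualifies. Sections 11.4.1 and 11.4.4 also do more than count AEs, since they plan confidence intervals and grade distributions for specific toxicities.

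Much of this stands. A reader might infer that symptomless Grade 3-4 cytopenias escape both the hold and the safety table. The documents do not support that for values found during dosing: the 6.6 rows carry no symptom condition, and both 7.1.1 and the 7.2.1 list count the resulting interruption. A reader might also call the rules circular, because 6.5 holds drug for an AE while 7.1.1 makes a value an AE because drug is held. For the three cytopenias, 6.6 breaks the circle: its reference to 6.5 is attached to resuming at a lower dose level, not to the hold. The circle remains only where 6.6 has no row.

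The defense does not reach the other three rows of the table. Whether those values are tabulated depends on opinion or on a follow-up action the protocol does not require. The planned intervals and grade distributions use the same Section 7 definition, so they do not restore what it leaves out.

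**Conclusion.** The point holds in limited form. CTCAE grade alone never makes a laboratory value an AE, the exclusive tests in 7.1.1 and 7.2.1 differ, and no analysis reads the laboratory results directly. For symptomless Grade 1-2 values, Grade 3-4 values of parameters without a 6.6 row, and values first seen after the last dose, incidence in the second primary endpoint is biased downward against measured grades. The relative shortfall equals the unrecorded share f, which the documents do not allow to be computed.

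This rests on three assumptions: that the 6.6 hold is applied on grade as written, that the intended quantity is the incidence of graded laboratory toxicity rather than of events judged clinically significant, and that recorded AEs are graded from the same laboratory values. If sites did not apply 6.6 as written, more would be lost, but that would be non-compliance and not a fault in the plan. The PSA50 analysis and the sample size are unaffected. It is a worthwhile, inexpensive improvement to the safety reporting.

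**What to change.** 1. In Section 11.4.1, add a table of worst on-treatment CTCAE v4.03 grade and of shift from baseline for each scheduled hematology and chemistry parameter. Derive it from the laboratory results, independently of AE recording. State that the window runs from first dose through the end-of-treatment visit, and define baseline. Appendix C schedules no laboratory tests on Cycle 1 Day 1, so baseline would be the screening value unless another sample exists.
2. Reconcile Sections 6.5, 6.6, 7.1.1 and 7.2.1 so that one definition says when a laboratory value is an AE, including for parameters with no row in 6.6. This should settle recording only. No hold, resumption or discontinuation rule is proposed here, and the rewording should not alter one by implication: making every Grade 3-4 value an AE, for example, could widen the 6.5 hold and discontinuation provisions.

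The first change corrects the reported laboratory rates however the second is resolved. The cost is protocol wording and one extra table from data already collected, with no new procedure. Reported laboratory toxicity rates will look somewhat higher, and the text should explain that the table and the AE tabulation measure different things.
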